**Corticosteroid Injections for the Treatment of Common Upper Extremity Pathologies,
With or Without Lidocaine: A Randomized Control Trial**

NTC# NCT03704584

Date: 7/9/2019

Project Summary

Title of Study: Corticosteroid Injections for the Treatment of Common Upper Extremity Pathologies, With or Without Lidocaine: A Randomized Control Trial

Principle Investigator: [name] MD

Co-Investigators: [name], [name], [name] MD, [name] MD, [name]

Study Coordinators: [name], [name], [name], [name]

Version date: 7/9/2019

Lay Summary: A tendon is a type of tissue that connects your muscles to your bones. These tissues help control actions such as running, jumping, grasping, and lifting. Without tendons, you wouldn't be able to control the movement of your body. A protective layer known as synovium covers tendons. This sheath produces fluid, which keeps the tendon lubricated and moving properly. Inflammation or swelling of the sheath is known as tendon sheath inflammation or tenosynovitis. This condition is often treated with an injection into or around the sheath. This injection often consists of a corticosteroid with or without lidocaine. Corticosteroid are drugs that decrease inflammation and are given for a number of orthopaedic conditions to decrease symptoms of the underlying disease. Lidocaine is also a drug that blocks the pain response, although it only blocks it momentarily. Our study aims to determine if corticosteroid injection alone is as effective as corticosteroid combined with lidocaine for the relief of tenosynovitis of the upper extremity.

Precis/Abstract:

This will be a randomized control trial to study the efficacy of a combined lidocaine and corticosteroid injection on pain, range of motion, and patient reported outcomes versus a corticosteroid injection alone for the treatment of common upper extremity tendinopathies and nerve entrapments that are often treated with a combination of these injectates. Patients will be assigned randomly to a control group (corticosteroid injection alone) or the treatment group (lidocaine plus corticosteroid injection). At the initial injection a 10-point likert scale prior to and after the injection will be administered. The patients will be followed up at 6 weeks after the injection, at which time the Visual Analog Scale for pain (VAS-pain), range of motion (ROM), and patient reported outcome data will be collected and any complications will be noted. Patients will also utilize a pain journal to track VAS-pain over the first 7 post-injection days. We hypothesize that those who receive lidocaine plus corticosteroid injection will be non-inferior in regards to pain, range of motion (ROM), failure of injection requiring surgery, and patient reported outcome scores compared with patients who received corticosteroid injection alone.

Background and Significance:

Tenosynovitis is a common ailment of the upper extremity resulting in pain around the affected joint due to injury to the tendon sheath. One of the most common manifestations of tenosynovitis is trigger finger. Trigger finger is an extremely common pathology encountered by primary care providers and hand surgeons. Reported incidence of 28 cases per 100,000 has been documented [1]. This entity occurs when the contents of the flexor tendon sheath do not fit cleanly

within the sheath, causing friction on movement of the fingers. Progression from a clicking or locking sensation to complete inability to flex or extend the finger (hence the designation “trigger finger”) occurs over the course of the disease. Therefore, triggering may not be initially noted on exam. Pain from this pathology can be experienced at the proximal interphalangeal joint, the metacarpophalangeal joint, or even the palm [2]. Reported increases in rates have been documented in diabetics, cases of repetitive trauma, those with renal and thyroid disease, and individuals with inflammatory conditions [3].

The cause of trigger finger is poorly understood, with early studies identifying the condition as a form of tenosynovitis on histologic analysis. More recent studies have identified a lack of inflammatory cells, suggesting an abnormality in proliferation of fibrocartilage rather than a primary inflammatory condition [4]. Treatment of trigger finger has been studied extensively, but few evidence based guidelines exist for the treatment of this disease process [1]. Current treatment modalities are diverse and numerous, including non-operative management (splinting, stretching techniques, heat therapy, electric stimulation therapy, acupuncture, corticosteroid injection, and high-intensity focused ultrasound aimed at degrading the fibrosis surrounding the tendon sheath) and operative management (with open, percutaneous, and endoscopic methodology all having been described) [1, 5]. In 2017, Amirfeyz *et al.* proposed an evidenced based treatment guideline for trigger finger, with the first line treatment listed as “steroid and local anesthetic injection” followed by open operative management upon either failure of corticosteroid injection or patient refusal of corticosteroid injection [1].

This treatment algorithm reflects existing research regarding treatment of trigger finger: corticosteroid injection for trigger finger has been studied extensively [6-25]. However, few well, randomized control trials have been undertaken comparing corticosteroid injection to placebo. Of the trials that have been done, both studies indicated improved outcomes with a combined injectate of corticosteroid with lidocaine versus just lidocaine alone [26, 27]. The long term efficacy of steroid injection is reasonable, with success rates as high as 69% [8]. That said, many patients will experience return of their symptoms and will go on to need open surgical treatment for recurrent trigger finger [3].

While several studies have compared corticosteroid injection with lidocaine to lidocaine injection alone, to date, no study has evaluated the effectiveness of a corticosteroid injection either with or without lidocaine. Our study aims to evaluate whether or not lidocaine in the injectate combined with corticosteroid improves patient reported outcomes and recurrence of pain and morbidity from trigger finger as compared with corticosteroid injection alone.

In addition, similar pathologies exist where the role of lidocaine remains vague. One such pathology is de Quervain tenosynovitis. de Quervain tendinopathy affects the abductor pollicis longus (APL) and extensor pollicis brevis (EPB) tendons in the first extensor compartment at the styloid process of the radius. It is characterized by pain or tenderness at the radial side of the wrist. Although de Quervain tendinopathy is often attributed to overuse or repetitive movements of the wrist or thumb, the cause is generally unknown. It most commonly affects women between the ages of 30-50 years old [28].

A small randomized trial found that glucocorticoid injections resulted in significantly better symptom improvement compared with placebo one week after injection [29]. Among those who responded to glucocorticoid injections, the beneficial effects were maintained during the 12-month follow-up period. Another randomized trial also found that splinting plus glucocorticoid injection was better than splinting alone [30]. Most patients experience pain relief after a single glucocorticoid injection [30, 31]. In patients with recurrent symptoms after initial relief with the

first glucocorticoid injection, a second injection may provide benefit. However, limited evidence is available about the role of lidocaine during these injections. We further aim to elucidate the role of corticosteroid and lidocaine versus corticosteroid alone in the treatment of de Quervain tenosynovitis.

Furthermore, the role of lidocaine with corticosteroid in the treatment of a number of other tenosynovitides remains ambiguous. These include tenosynovitis of the shoulder, biceps, elbow, wrist, thumb, carpometacarpal, midcarpal, elbow, and small joints of the hand (PIP, DIP, MP). We aim to ascertain whether the corticosteroid and lidocaine injectate together is as effective as corticosteroid in the treatment of these tenosynovitides. For all these pathologies corticosteroid with or without lidocaine is standard of care for orthopaedic hand and shoulder surgeons and the use of either treatment regimen is based on personal preference by the surgeon.

Objectives:

1. Determine differences in pain scores / likert scale at the time of injection and during follow up in the corticosteroid plus lidocaine group as compared to the corticosteroid alone group.
2. Determine differences in range of motion of the affected joint in the corticosteroid plus lidocaine group as compared to the corticosteroid alone group.
3. Determine differences in patient-reported outcome scores (VAS-pain, qDASH, PRWE, ASES, SF12, EQOL) in the corticosteroid plus lidocaine group as compared to the corticosteroid alone group.
4. Report patient characteristics associated with efficacy of addition of lidocaine to corticosteroid injectate for pain and ROM resolution (type of injury, affected joint, age, BMI, comorbidities, etc.).

Hypotheses:

Hypothesis⁰: Corticosteroid injectate alone will result in statistically significant reduced pain scores as compared to corticosteroid with lidocaine for the treatment of tenosynovitis.

Hypothesis¹: Lidocaine plus corticosteroid injectate will result in equivalent requirements for repeat injection or conversion to surgery as compared with corticosteroid injectate alone for the treatment of tenosynovitis.

Hypothesis²: Lidocaine plus corticosteroid injectate will result in equivalent patient reported outcomes scores as compared to corticosteroid alone for the treatment of tenosynovitis.

Hypothesis³: Lidocaine plus corticosteroid injectate will result in equivocal patient-reported outcome scores, ROM, and pain reduction as compared to corticosteroid alone for the treatment of tenosynovitis.

Study Design

This will be a randomized control trial of a group of patients with upper extremity tenosynovitides treated with either lidocaine plus corticosteroid or corticosteroid injection alone by upper extremity fellowship trained surgeons at Emory University. Patients will be randomly assigned to one of two groups at the time of treatment: 1. Lidocaine Plus Corticosteroid and 2. Corticosteroid Alone. A random allocation sequence, concealed in consecutively numbered, opaque, sealed envelopes, determining active treatment or placebo, will be computer generated. Written-informed consent will be obtained from patients prior to injection.

Patients in the Corticosteroid group will be treated with a 40 mg/mL injection of corticosteroid following sterile preparation. The volume of injectate differs for each tenosynovitis being treated. For example, trigger finger patients in the corticosteroid alone group will receive a 1mL of injectate total (consisting of 1 mL of 40mg/mL triamcinolone).

Patients in the Corticosteroid and Lidocaine group will be treated with a 40 mg/mL injection of corticosteroid combined with 1% lidocaine. The volume of injectate differs for each tenosynovitis being treated. For example, patients being treated for trigger finger will receive 0.5 mL of 1% lidocaine and 1 mL of 40mg/mL triamcinolone.

Needle size and insertion site of needle differs for each tenosynovitis being treated. For trigger finger specifically, needle injections will be performed with an appropriately sized needle inserted over the A1 pulley at a 45-degree angle. The injection will be done with the same technique for both groups by the attending physician. The medication will be injected extra-synovially in order to make the treatment more reproducible. This method of injection has been supported in previous studies.

Outcome Measures:

- Likert Scale: A 10-point likert scale will be asked before and after injection which has been previously validated in other studies looking at efficacy and pain surrounding injections of the upper extremity.
- Pain Assessment: A pain assessment will be assessed before performing the injection, at the time of injection, and at each subsequent follow up visit. Pain scores will be obtained via the Visual Analog Pain Scale (VAS-pain), which is ranked from 0 (no pain) to 10 (highest amount of pain). Pain will be assessed at rest and active movement of the affected joint. Patient will also be asked to fill out the VAS-pain score twice daily in a pain journal (once in the morning and once at night) each day until post-injection day 7.
- qDASH/PRWE/ASES/SF12/EQOL score: These scores will be administered at each clinic follow up. They will also be administered 6 week after the injectate has been performed.
- Need for subsequent reinjection and surgical operation will be recorded.

These scores, specifically the 10-point likert, will also be assessed before performing the injection, immediately after the injection, and again at the various follow up appointments. During clinic follow up we will monitor for complications.

Inclusion Criteria:

- All adult clinical patients of Emory upper extremity surgeons undergoing injection for treatment of the following who are willing to participate in the study will be included in the study: Tenosynovitis of the upper extremity, including but not limited to, the shoulder, biceps, elbow, wrist, thumb, carpometacarpal, midcarpal, elbow, and small joints of the hand (PIP, DIP, MP).
- Between the ages of 18 years and 95 years.

- For trigger finger: patients with a diagnosis of stenosing tenosynovitis based on a history of triggering and the presence of tenderness over the A1 pulley upon clinical examination. All patients, based on the Quinnell grading of trigger finger see in the figure below, will be included.

Grade	Clinical findings (during flexion and extension)
0	Normal movement
I	Uneven movement
II	Actively correctable
III	Passively correctable
IV	Fixed deformity

Exclusion Criteria:

- Patients who are minors, vulnerable subjects, or who are not willing to consent to participate in the study.
- Allergies to glucocorticoids, current daily use of glucocorticoids or strong opioids (morphine, fentanyl, hydromorphone, ketobemidone, methadone, nicomorphine, oxycodone, and meperidine), severe diabetic neuropathy of the hand influencing pain perception, rheumatoid arthritis, and neurological or psychiatric diseases, potentially influencing pain perception.
- Subjects who, in the opinion of the investigator, may be non-compliant with study schedules or procedures.

Statistical Analysis:

Data will be stored on an excel spreadsheet. We will collect the name, medical record number, age at time of surgery, ethnicity, gender, BMI, presence of diabetes, Quinnell grading of trigger finger, smoking status, pre-injection VAS-pain, post-injection VAS-pain, 10 point likert scale, complications, and need for repeat injection or surgical release. It is possible that other variables may be added depending on analysis. Each variable will be used as a nominal variable when possible (e.g. smoking status) or a continuous variable if needed (e.g. VAS-pain, patient related outcome scores). For some statistical calculations we may break up the continuous variables in to ranges (e.g. Ages 15-20, 25-30). We will perform statistical analysis using unpaired, 2-tailed Student t test to compare means for normally distributed data, Kruskal-Wallis test to compare medians of non-normally distributed data, and chi-square test to compare proportions. Statistical significance will be interpreted as $P < .05$. Confidence intervals will be calculated with a confidence level of 95%.

Specifically, the 2 groups will be compared using the Mann-Whitney U test to analyze the difference between the post-injection VAS scores. The Wilcoxon sign-rank test will be used to test the difference between the treatment and control group for pain and patient related outcomes.

The minimally clinically important difference (MCID) varies for each outcome measure. Therefore, for the purposes of a power analysis, we will use the VAS-pain at the time of injection as the primary outcome. A similar study was published in 2017 from Earp *et al.* comparing needle-free jet lidocaine for pre-corticosteroid injection anesthesia with simultaneous lidocaine and corticosteroid injection. Using the results of this study as a metric, for the purposes of our study, to determine a 1-point change in VAS (4.5 to 3.5) with the reported standard deviation of 2 (SEM

was 0.4, with 30 subjects in each group) in the Earp *et al.* study, the number needed to treat to detect a difference between the treatment and placebo group would be 63 [32]. Therefore, we aim for a sample size of 63 patients for each possible tenosynovitis described in the inclusion criteria.

In total, **we plan to enroll 1000 patients total into this study** when combining all possible tenosynovitides encountered at Emory. These outcomes will be feasible to obtain in a reasonable time frame given the high volume of patients treated for tenosynovitis of all types at Emory. Patients will be grouped together for analysis and also broken into subgroups for sub-analysis based on primary diagnosis for injection.

JMP Pro Software or SPSS will be used to analyze the data and perform the statistics.

Risks to participation

Risks to participation include breach of confidentiality from PHI used to conduct the study. Every effort will be used to scrub data when possible and to use subject numbers/unique identifiers when possible.

As stated above, the first line treatment for trigger finger is corticosteroid injection with lidocaine, although there are a significant proportion of hand surgeons who inject corticosteroid alone. As no study has evaluated the efficacy of lidocaine mixed with the injectate versus corticosteroid alone, our study does not constitute deviation from current status quo of best medical practice for the treatment of trigger finger. **Both treatment options are considered standard of care and it is solely based on physician preference for which regimen is chosen as an injectate.** Patients will be notified of any potential risks with signed written consent as they would before any standard corticosteroid injection for the treatment of trigger finger. They will also be asked to sign an additional consent form agreeing to participate in our study outlining the nature of the study and the fact that no deviation from current best medical practice will occur throughout the course of the study.

Benefits to future subjects or science

By identifying whether or not lidocaine combined with corticosteroid injectate leads to improved patient outcomes as compared with corticosteroid injection alone, we will be able to educate physicians and patients on best medical practice for treatment of trigger finger. Additionally, as lidocaine has been reported to cause significant burning during injection, if there is no additional benefit to addition of lidocaine to corticosteroid injection, we will be able to spare future patients the discomfort of combining the injectate with lidocaine.

Data safety and monitoring plan:

Patients will be followed up closely in clinic at 2 weeks and 6 weeks post-injection to ensure patients did not experience side effects from the injection and to assess for efficacy of the injection. A low dose of corticosteroid and lidocaine is being utilized and we do not anticipate adverse effects.

Patients will have the ability to remove themselves from this study either completely or partially, and these options will be elucidated on the written consent form.

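### No pre-injection range of motion is scheduled, so the ROM part of Objective 4 cannot be measured as written; the questionnaire baseline is unclear

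*Combined protocol and SAP*

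**What the plan says.** - **Objectives and Hypotheses.** Objective 2 compares ROM between the arms. Objective 4 looks for characteristics associated with "efficacy of addition of lidocaine to corticosteroid injectate for pain and ROM resolution". Hypothesis 3 also names ROM.
- **Precis/Abstract.** The timing is "The patients will be followed up at 6 weeks after the injection, at which time the Visual Analog Scale for pain (VAS-pain), range of motion", and from the mention of ROM the sentence runs on as "range of motion (ROM), and patient reported outcome data will be collected and any complications will be noted". The only measure it places at the injection visit is the Likert scale: "At the initial injection a 10-point likert scale prior to and after the injection will be administered".
- **Outcome Measures.** The list covers the Likert scale, VAS-pain, the five questionnaires (qDASH, PRWE, ASES, SF12, EQOL), and reinjection or surgery. ROM is not on it. The VAS-pain bullet states a reading before injection. The questionnaire bullet says "These scores will be administered at each clinic follow up" and adds the 6-week point. A paragraph after the list says "These scores, specifically the 10-point likert, will also be assessed before performing the injection", followed by a reading straight after injection and readings at follow-up.
- **Statistical Analysis.** The list of collected data ends with "pre-injection VAS-pain, post-injection VAS-pain, 10 point likert scale, complications, and need for repeat injection or surgical release". Neither ROM nor any of the five questionnaires is on it, although the section allows variables to be added. The planned tests are the t test, Kruskal-Wallis, chi-square, Mann-Whitney and Wilcoxon signed-rank tests. No model with a baseline covariate is planned for any outcome. Patients are to be analysed together and also by primary diagnosis.

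**The concern.** Resolution is a change from a starting state. If ROM is read only at 6 weeks, a joint that recovered cannot be told apart from one that was never restricted, and a missed pre-injection reading cannot be recovered later. The ROM half of Objective 4 would then have no data.

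The questionnaires raise a lesser version of the same problem. If sites follow the bullet alone, no baseline is taken; if they follow the paragraph after the list, it may be. Different staff could reasonably do different things.

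The pooled analysis adds to this. Eligible sites run from the shoulder to the small joints of the hand, so raw 6-week ROM across all patients will largely reflect which joint was treated. With neither the starting value nor the joint in the model, that spread stays in the error term of the comparisons behind Hypotheses 2 and 3.

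**Working it through.** **1. Stated measurement times, by outcome.**

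| Outcome | Before injection | After injection | On the data list |
|---|---|---|---|
| Likert | Yes (Precis, Outcome Measures) | Yes | Yes |
| VAS-pain | Yes (Outcome Measures, data list) | Yes | Yes |
| Five questionnaires | Unclear (bullet silent; later paragraph may cover them) | Follow-up visits and 6 weeks | No |
| ROM | Nowhere | 6 weeks (Precis only) | No |

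**2. ROM.** The one sentence that could add a baseline, the paragraph closing Outcome Measures, refers to scores. ROM is not a score and is not in the list that the paragraph follows. Even the generous reading therefore supplies no pre-injection ROM, and change in ROM cannot be formed from one reading.

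**3. Questionnaires.** Two readings are open. The plural wording and the position after the whole list favour a baseline for every score. Against that, the paragraph singles out the Likert scale, its times begin with those the Precis gives for the Likert scale, and taken literally it would have all five questionnaires repeated immediately after the injection. The signed-rank test named for patient-related outcomes is a paired test, which would suit before-and-after values. However, the plan assigns it to the comparison of treatment with control, so it does not settle the matter.

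**4. The plan's own sample-size figure.** Inputs from Statistical Analysis are a difference of 1 point on VAS-pain, SD 2 and two-sided alpha 0.05. Power of 80% and 1:1 allocation are assumed, as neither is stated.

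n per arm = 2 × (1.960 + 0.842)² × 2² / 1² = 62.8, rounded up to 63.

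This matches the stated 63 as a per-arm number. It concerns VAS-pain at injection and uses no ROM or questionnaire data, so the present point leaves it unchanged.

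**5. Precision forgone.** With correlation r between baseline and 6-week values, using the baseline as a covariate multiplies the variance by 1 − r². The equivalent gain in patients is 1/(1 − r²).

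- r = 0.5: 1 − 0.25 = 0.75; 1/0.75 = 1.33.
- r = 0.7: 1 − 0.49 = 0.51; 1/0.51 = 1.96.

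A simple change score has variance factor 2(1 − r), which is 1.00 at r = 0.5 and 0.60 at r = 0.7. It gains less than the covariate at both values, and nothing at r = 0.5.

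These are relative figures. The plan gives no SD, target difference or correlation for ROM or any questionnaire, so no power can be calculated for those outcomes. The further gain from including the joint cannot be sized either.

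**The case against.** The Precis is a summary and an incomplete one. Apart from the Likert scale and the 7-day journal, it mentions VAS-pain only at 6 weeks, yet Outcome Measures gives VAS-pain a pre-injection reading. The data list is not a visit schedule: it omits the questionnaires at every time point and is open-ended. Silence in either place is weak evidence that a baseline will not be taken. This stands for the questionnaires, and it is why the point on them is ambiguity, not absence. It does not help ROM, because no other section supplies a time for it, and permission to add variables does not schedule a measurement.

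A reader might infer that all patient-reported scores are taken only after injection. The plan does not support that. Objective 3 counts VAS-pain among those scores, and its baseline is explicit; for the five questionnaires the text can be read either way.

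A reader might also infer that the trial loses a baseline adjustment, or that the 6-week comparisons fail. None is planned, even for VAS-pain, so the adjustment is an option not taken. Randomisation keeps the comparison of 6-week ROM in Objective 2 valid without a baseline, though it is less precise and baseline balance in ROM cannot be checked.

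The mix of joints is partly met by the planned analysis by primary diagnosis, and Quinnell grade gives a coarse record of movement in trigger finger. Both stand, but neither helps the pooled analysis of other joints, and a grade is not a ROM reading.

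**Conclusion.** The concern holds in two parts. First, no pre-injection ROM is scheduled, so the ROM half of Objective 4 cannot be answered if the plan is followed as written. That loss is complete, but it is confined to part of a descriptive objective. Second, the plan does not make clear whether the five questionnaires have a baseline.

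The between-arm comparisons at 6 weeks remain valid. What they forgo is precision: a variance factor of 0.75 to 0.51, worth about 1.3 to 2.0 times as many patients. This rests on assumed correlations of 0.5 to 0.7 and on a roughly linear relation between baseline and follow-up. The plan's powered outcome is not touched. The change should be made because it is cheap and the missing reading cannot be obtained afterwards.

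**What to change.** - In Outcome Measures, list ROM of the affected joint as an outcome. State that ROM and all five questionnaires are collected at the injection visit before the allocation envelope is opened, and again at 6 weeks. Reword the paragraph after the list so that it says which scores it covers.
- In Statistical Analysis, add ROM and the questionnaires, with their time points, to the list of collected data.
- Define ROM resolution from the two readings before any data are seen.
- Compare 6-week ROM and questionnaire scores between arms with the baseline value and diagnosis (joint) as covariates.

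The cost is a slightly longer baseline visit. No extra visit is needed, since patients already attend for the injection.

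### Non-inferiority and equivalence are claimed, but no margin or confidence-interval rule is set, so the planned difference tests cannot establish them when the arms are similar

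*Combined protocol and SAP*

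**What the plan says.** Several kinds of claim stand side by side.

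- **Non-inferiority.** Precis/Abstract: "We hypothesize that those who receive lidocaine plus corticosteroid injection will be non-inferior in regards to pain", continuing to range of motion, failure requiring surgery and patient-reported outcomes.
- **Equivalence.** Hypothesis 1: "Lidocaine plus corticosteroid injectate will result in equivalent requirements for repeat injection or conversion to surgery as compared with corticosteroid injectate alone". Hypothesis 2: "Lidocaine plus corticosteroid injectate will result in equivalent patient reported outcomes scores as compared to corticosteroid alone". Hypothesis 3: "Lidocaine plus corticosteroid injectate will result in equivocal patient-reported outcome scores, ROM, and pain reduction as compared to corticosteroid alone"; I read its adjective as a slip for equivalent.
- **Equal effectiveness, in opposite directions.** Lay Summary: "Our study aims to determine if corticosteroid injection alone is as effective as corticosteroid combined with lidocaine". Background and Significance, on sites other than trigger finger and de Quervain: "We aim to ascertain whether the corticosteroid and lidocaine injectate together is as effective as corticosteroid in the treatment of these tenosynovitides".
- **Difference.** Background and Significance, on trigger finger: "Our study aims to evaluate whether or not lidocaine in the injectate combined with corticosteroid improves patient reported outcomes". Hypothesis 0: "Corticosteroid injectate alone will result in statistically significant reduced pain scores as compared to corticosteroid with lidocaine". Objectives 1 to 3 also ask about differences.

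Statistical Analysis lists the t test, Kruskal-Wallis, chi-square, Mann-Whitney and Wilcoxon tests, with significance at P<.05. It says that 95% confidence intervals will be calculated but compares them with nothing. The same section names VAS-pain at the time of injection as primary for the power analysis and sizes the trial to detect a 1-point difference. It remarks that the minimally important difference varies by outcome but gives no values. No margin appears anywhere.

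**The concern.** A test of no difference can reject equality; failing to reject does not establish similarity. Non-inferiority needs the unfavourable limit of a confidence interval to stay short of a stated margin, and equivalence needs the whole interval inside two margins. The plan has neither. A significant result favouring the test arm would imply its non-inferiority on that outcome, but could not show equivalence. When the arms are similar, which is what most of the hypotheses predict, no planned rule leads to the hypothesised conclusion.

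The document does not say that P>.05 will be read as equivalence, but it leaves that as the tempting substitute. The substitute errs in both directions: small diagnosis groups will often miss a real difference, while the pooled comparison may declare a trivial difference significant and so appear to refute equivalence. Benefits to future subjects or science envisages dropping lidocaine if it adds no benefit, and that conclusion needs the missing rule in the Lay Summary's direction (steroid alone against the combination). A margin chosen after the arms have been compared would not be credible.

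**Working it through.** **Inputs.** From Statistical Analysis: difference 1 VAS point, SD 2, two-sided 0.05, 63 per diagnosis, 1000 in total. Assumed because not stated: equal allocation, 80% power (it reproduces the 63), and every margin below. Whether 63 is per arm or per diagnosis in total is not stated, so both are shown (63+63 and 31+32).

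**1. The plan's own figure.** n per arm = 2 × SD² × (1.960 + 0.842)² / difference² = 2 × 4 × 7.849 / 1 = 62.8, so 63 per arm. This is the size for a two-sided difference test. The 1-point figure is therefore a difference to detect on injection-time VAS, not a margin.

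**2. Chance of P<.05 favouring the test arm when the true difference is 0.** 0.05 / 2 = 2.5% at any size (t test).

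**3. How often P>.05 occurs despite a real difference.** Two-sample t test, noncentrality = difference / SE, with SE = SD × √(1/n₁ + 1/n₂). At SD 2, SE = 0.356 for 63+63 and 0.504 for 31+32. For a true 1 point the noncentralities are 2.81 and 1.98, against critical values of 1.98 and 2.00.

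| Test and SD | 63+63, true 1 | 63+63, true 0.5 | 31+32, true 1 | 31+32, true 0.5 |
|---|---|---|---|---|
| t test, SD 2 | 20% | 71% | 50% | 84% |
| Mann-Whitney, SD 2 (40,000 simulated trials, normal data) | 23% | 73% | 53% | 85% |
| t test, SD 2.19 | 28% | 75% | 57% | 86% |

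The SD of 2.19 is 0.4 × √30, from the standard error and group size quoted in the plan. By contrast, a 95% interval rule with an assumed 1-point margin would wrongly claim non-inferiority in 2.5% of comparisons when the true disadvantage is 1 point.

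**4. The opposite error when pooled.** At 500 per arm, SE = 2 × √(2/500) = 0.126. With a true difference of 0.25, P<.05 occurs in 51% of trials (44% at SD 2.19), yet the 95% interval lies within ±1 point in over 99.9%.

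**5. Power if margins were stated.** True difference 0. Non-inferiority: one-sided 0.025, noncentrality = margin / SE. Equivalence: probability that the whole interval lies within the margins, integrated over the sample SD.

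| Size, margin, SD | Non-inferiority | Equivalence, 90% CI | Equivalence, 95% CI |
|---|---|---|---|
| 63+63, 1 point, SD 2 | 80% | 75% | 59% |
| 31+32, 1 point, SD 2 | 50% | 25% | 5% |
| 500+500, 1 point, SD 2 | >99.9% | >99.9% | >99.9% |
| 500+500, 0.5 point, SD 2 | 98% | 98% | 95% |
| 500+500, 0.5 point, SD 2.19 | 95% | 95% | 90% |
| 450+450 (assumed 10% loss), 0.5 point, SD 2 | 96% | 96% | 93% |

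For 80% equivalence power in one diagnosis at a 1-point margin and SD 2, about 70 per arm (90% CI) or 86 per arm (95% CI) are needed.

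**The case against.** The strongest reply is that the named primary outcome, Objectives 1 to 3 and Hypothesis 0 are difference questions that the planned tests serve, and that the plan nowhere promises to treat P>.05 as equivalence. Both points stand. They narrow the concern but leave the abstract's only hypothesis and Hypotheses 1 to 3 without a decision rule.

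It can also be said that the calculations use injection-time VAS-pain, whose difference test is not in dispute, and that the power figures and non-inferiority claim rate need a margin the plan does not give. That is fair. The pain claims name no time point, and the other outcomes have no SD or event rate, so the figures illustrate the size of the problem on the only outcome with usable inputs. The gap itself does not depend on them.

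The 2.5% is a t-test result. For a chi-square test at an assumed 2% event rate it is lower: 1.1% at 63 per arm and 0.2% at 31+32. This makes the planned route to non-inferiority on reinjection or surgery narrower still.

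Finally, stating margins is not free of consequence. At 63 per arm, SD 2 and a 0.5-point margin, non-inferiority power is 28% (16% if 63 is the total) and equivalence power is practically nil. At SD 2.19 and a 1-point margin, non-inferiority power is 72% or 43%, and 90%-interval equivalence power 63% or 13%. This stands as a caution about per-diagnosis claims. It does not excuse the missing rule.

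**Conclusion.** The concern holds and must be fixed. The non-inferiority, equivalence and equal-effectiveness claims have no margin and no interval rule, so the plan cannot establish them when the arms are similar.

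The illustration on VAS-pain rests on normal data, equal arms, and an SD of 2 or 2.19. Per diagnosis, non-significance would accompany a true 1-point difference in 20% to 57% of comparisons, depending on the SD, the test and the reading of 63. In the pooled trial, a 0.25-point difference would be significant about half the time at SD 2. Range of motion, patient-reported outcomes and reinjection or surgery cannot be quantified from the document.

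Two related points need settling. The Lay Summary and the Background set opposite reference arms. Hypothesis 0 predicts lower pain with steroid alone, while the abstract and Hypothesis 3 predict non-inferior or equivalent pain; without time points or a margin it is unclear whether these conflict.

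**What to change.** 1. Use one direction and one reference arm throughout the Lay Summary, Abstract, Background, Hypotheses and Benefits sections, and give Hypotheses 0 and 3 a time point. Keep the difference tests for Objectives 1 to 3 and Hypothesis 0.

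2. For each outcome, including pain, do one of the following before outcomes are compared by arm.
   - Pre-state and justify a margin, and add to Statistical Analysis: *Non-inferiority will be concluded only if the 95% CI limit for test minus reference on the unfavourable side does not reach [margin]; equivalence only if the whole pre-stated interval (90% for two one-sided tests at 0.05, or 95%) lies within the margins; P>.05 is not evidence of equivalence.* Name the effect measure and interval that will accompany the rank tests.
   - Delete the non-inferiority or equivalence wording for that outcome and report the difference with its 95% CI, drawing no equivalence claim from P>.05.

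3. State whether each claim concerns the pooled or the per-diagnosis comparison; Statistical Analysis plans both.

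**Cost.** The change is to wording and needs no extra patients. Deletion needs no margin. Keeping the claims means justifying margins for range of motion, several scores and event rates, which takes real work. On VAS-pain, the pooled 1000 supports a margin of 1 or 0.5 point. Per-diagnosis claims may be inconclusive unless groups are enlarged, and a non-significant difference can no longer be reported as equivalence.
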